## **6.9 Drug Accountability**

The Investigator, or the designated/authorized representative, is responsible for the management of all the study medications to be used for the study. Study medications that should be stored in a locked, secure storage facility with access limited to those individuals authorized to dispense the study medications.

An inventory will be maintained by the Investigator or pharmacist (or other designated individual), to include a signed account of all the study medication(s) received and dispensed during the trial.

At the conclusion or termination of the study, the Investigator or the pharmacist shall conduct and document a final drug supply (used and unused) inventory. An explanation will be given for any discrepancies.

All the study medications supplied, used or unused, will be destroyed directly from the Investigator by the centre. In this case, a destruction certificate must be asked to the investigational centre and filed both at site and at Sponsor. Destruction will not occur until authorized by Chiesi.

## **6.10 Provision of additional care**

N.A.

Clinical Study Code: CLI-06001AA1-02	Version No.: 1.0
EUDRACT No.: 2020-004201-31	Date: 19 October 2020

## 7. STUDY PLAN

### 7.1 Study Schedule

	Screening	Treatment Period				Follow-up
		Day -1	Day 1	Day 2-10	Day 11	
Informed consent	X					
Residential period		X	X	X		
Discharge					X	
Treatment intake						
IMP administration				X 		
Training						
Training with In-Check Dial	X	X	X			
Training with Placebo	X	X	X			
Subject Health Evaluation						
In/Ex Criteria	X	X				
Medical History	X					
Demographic data	X					
Height and weight	X					
Alcohol breath test	X	X				
Physical examination	X	X			X 	
Adverse Events recording	X	X	X	X	X	X
Restrictions	X	X	X	X	X	
Concomitant Med	X	X	X	X	X	X
Safety assessment in blood						
Clinical Chemistry	X				X 	
Serology	X					
Haematology	X				X 	
Fasting glucose	X				X 	
Generic assessments in urine						
Urinalysis	X					
Drug panel	X	X				
Cotinine	X	X				
Samples for PK evaluations a						
Blood			X	X	X	
Urine		X	X	X	X	

Clinical Study Code: CLI-06001AA1-02	Version No.: 1.0
EUDRACT No.: 2020-004201-31	Date: 19 October 2020

	Screening	Treatment Period				Follow-up
		Day -1	Day 1	Day 2-10	Day 11	
Feces		X	X	X	X	
Cardiac assessmentsb						
Local ECG	X		X			
Vital Signs - Blood Pressure	X		X			
Pulmonary Assessment						
Spirometry	X					

Footnotes for Evaluation Schedule:

1. There will be 2 types of administration:
  - 4 inhalations of CHF6001 800 $\mu$ g/20mg DPI NEXThaler®
  - Intravenous infusion for 15min of the tracer starting 1h45min after the inhaled dose (time of the first inhalation) and ending at the expected  $T_{max}$  of 2 h for the inhaled dose
2. A full physical examination and collection of blood safety test will be performed at discharge. A follow-up visit will be done only if deemed necessary by the principal investigator.

a) Pharmacokinetic samples will be collected as:

- **Blood samples** for plasma non-radiolabeled CHF6001 to be collected at pre-dose (within 60 min from inhaled dosing) and at the following timepoints post inhaled dose: **15, 30, 60, 90 min, 2, 3.75, 5.75, 7.75, 9.75, 11.75, 13.75, 25.75, 49.75, 73.75, 97.75, 121.75, 145.75, 169.75, 193.75, 217.75 and 241.75 hours.**
- **Blood samples** for plasma [C]-total, [C]-CHF6001, [C] of the relevant metabolites to be collected at pre-dose (within 60 min from inhaled dosing) and at the following timepoints relative to the start of the IV infusion: **5, 10, 15 [end of infusion], 20, 25, 30, 45, 60 min, 2, 4, 6, 8, 10, 12, 24, 48, 72, 96, 120, 144, 168, 192, 216 and 240 hours.**
- **Blood samples** for whole blood [C]-total and [C]-CHF6001 at pre-dose (within 60 min from inhaled dosing) and **20 min after start of infusion**
- **Urine samples** for assessments of [C]-total, [C]-CHF6001 and [C] of the relevant metabolites to be collected at pre-dose from -12 hours to immediately before study drug inhaled administration (-12-0h) and at the following time frames relative to the start of the IV infusion: **0-4h, 4-8h, 8-12h, 12-24h, 24-48h, 48-72h, 72-96h, 96-120h, 120-144h, 144-168h, 168-192h, 192-216h and 216-240h.**
- **Fecal samples** for assessments of [C]-total, [C]-CHF6001 and [C] of the relevant metabolites to be collected at pre-dose from check-in (Day -1) to immediately before study drug inhaled administration (check-in -0h) and at the following time frames relative to the start of the IV infusion: **0-24h, 24-48h, 48-72h, 72-96h, 96-120h, 120-144h, 144-168h, 168-192h, 192-216h and 216-240h.**

b) Cardiac assessments will be performed at Screening and on Day 1 the treatment period as:

- **Local 12-lead ECG:** A triplicate ECG will be done for assessing eligibility at screening and a single ECG will be performed for general safety at predose and at 2,5 hours post dose (inhaled administration).
- **Vital Signs - BP:** BP measurement will be performed in triplicate at the following time points: at Screening and, for general safety, at predose and at 2,5 hours post dose (inhaled administration).

### 7.1.1 Screening

A Screening visit will be carried out from 3 to 31 days prior to the first administration of the study drug, in order to identify eligible consenting subjects for the study.

The following procedures will take place:

Clinical Study Code: CLI-06001AA1-02	Version No.: 1.0
EUDRACT No.: 2020-004201-31	Date: 19 October 2020

- Collection of the signed written INFORMED CONSENT by potential eligible subjects, after the study has been fully explained by the investigator or designee. The investigator or his/her designee should provide the participants ample time and opportunity to inquire about details of the trial and to decide whether or not to participate in the trial;
- SUBJECT SELECTION: inclusion/exclusion criteria will be checked
- SUBJECT TRAINING: subjects will be trained on a proper use of the inhaler with the In-Check Dial and the DPI Nexthaler® placebo.
- MEDICAL/SURGICAL HISTORY AND CONCOMITANT DISEASES: subject health history will be recorded.
- DEMOGRAPHY DATA COLLECTION: demographic data including age, gender and race, will be recorded.
- HEIGHT AND WEIGHT: will be recorded.
- ALCOHOL BREATH TEST: will be performed
- PHYSICAL EXAMINATION: a comprehensive physical examination will be performed.
- ADVERSE EVENTS RECORDING: AEs occurred since the signature of the informed consent will be recorded. In case of any clinically significant abnormality revealed during the physical examination or screening procedures, it will be recorded in the subject's medical history, unless its start date/time is after the informed consent signature date/time and it is not due to a pre-existing condition. In the latter case, it will be recorded as an adverse event.
- STUDY RESTRICTIONS: study restrictions criteria will be checked.
- PRIOR and CONCOMITANT MEDICATIONS CHECK: Any enzyme-inducing drugs, enzyme-inhibiting drugs, biologic drugs or any drug known to have a well-defined potential for hepatotoxicity (e.g. isoniazide, nimesulide, ketoconazole) taken in the last 3 months and any drug treatment, including prescribed or OTC medicines, vitamins, homeopathic remedies taken in the last 2 weeks will be recorded.
- BLOOD TESTING: blood samples collection for safety evaluations (clinical chemistry, haematology, serology, fasting glucose), according to section [7.2.2](#). Subjects have to be in fasting condition from at least 10 hours before blood samples are collected.
- URINE TESTING: urine samples collection for urinalysis, drug panel and cotinine test will occur according to section [7.2.3](#).
- LOCAL SAFETY ECG: Triplicate 12-lead ECG will be used to measure heart rate (HR) and will occur according to section [7.2.5](#).
- BLOOD PRESSURE: measurement of Systolic and Diastolic Blood Pressure (SBP and DBP) will occur according to section [7.2.4](#).
- SPIROMETRY: Lung function (FEV1 (L), FEV1 % of predicted normal value, FVC (L), FVC % of predicted normal value, FEV1/FVC) will be measured according to section [7.2.6](#).

## 7.1.2 Treatment Period

The subject will arrive at the clinical site on Day -1 and will stay overnight until the accomplishment of the 240 hours post-dose (i.v.) study procedures. All subjects will be discharged on Day 11.

Clinical Study Code: CLI-06001AA1-02	Version No.: 1.0
EUDRACT No.: 2020-004201-31	Date: 19 October 2020

- On Day -1, subjects will be hospitalised and will undergo the planned assessments and checks to confirm eligibility)
- On Day 1 of treatment period, subjects will undergo pre-dose assessments, then will receive the treatment and will start post-dose assessments.
- From Day 2 until Day 11, subjects will continue the post-dose assessments. Subjects will be instructed to continue to follow study restrictions (see section [7.1.4](#)). They will then be discharged soon after the 240h post-dose (i.v.) assessment.

The following procedures and assessments will take place during this period:

- SUBJECT TRAINING with devices: subjects will be trained on a proper use of the inhaler with In-Check Dial (Day -1/Day 1) and with the DPI placebo training kit (Day -1 and Day 1 pre-dose)
- SUBJECT SELECTION (Day -1): Inclusion criterion 6 and Exclusion criteria 7, 8, 9, 10, 11, 12 and 20, will be re-checked as requested in section [4.2](#) and [4.3](#). Subjects not fulfilling the mentioned criteria will be Screen Failed
- ALCOHOL BREATH TEST (Day -1): will be performed
- PHYSICAL EXAMINATION (Day 1): a full physical examination will be performed and any new revealed clinically significant abnormality since the screening visit will be recorded as an AE. Furthermore, a full physical examination will be performed at discharge.
- ADVERSE EVENTS RECORDING (Day -1 to Day 11): Any new AE/SAE occurred since the screening visit will be checked and recorded in the eCRF. The status of ongoing AEs will be checked and updated in the eCRF when applicable. Moreover, during this period in case of any new clinically significant abnormality revealed during the examination or procedures, it will be recorded as an adverse event.
- STUDY RESTRICTIONS (Day -1 to Day 11): study restrictions criteria will be checked.
- CONCOMITANT MEDICATIONS CHECK (Day -1 to Day 11): concomitant medications taken by the subject in the last 14 days and during the treatment period will be checked and recorded in the eCRF.
- BLOOD TESTING (at discharge): blood samples collection for safety evaluations (clinical chemistry, haematology, fasting glucose), according to section [7.2.2](#). Subjects have to be in fasting condition from at least 10 hours before blood samples are collected.
- URINE TESTING (Day -1): urine samples collection for drug panel and cotinine test will occur according to section [7.2.3](#).
- IMP ADMINISTRATION (Day 1)
- PK INVESTIGATION: Collection of blood (Day 1 to Day 11), urine and fecal samples (Day -1 to Day 11) for PK assessment will occur according to section [7.2.1](#).
- LOCAL SAFETY ECG: (Day 1) A single 12-lead ECG measurement will be performed on Day 1, at predose and at 2,5 hours post dose.
- BLOOD PRESSURE (Day 1): measurement of Systolic and Diastolic Blood Pressure (SBP, DBP) will occur according to section [7.2.4](#).

Clinical Study Code: CLI-06001AA1-02	Version No.: 1.0
EUDRACT No.: 2020-004201-31	Date: 19 October 2020

### 7.1.3 Follow-up

A follow-up call will be performed from 7 to 10 days after the discharge to perform the following:

- CONCOMITANT MEDICATIONS CHECK: concomitant medications taken to treat AEs by the subjects since the discharge will be checked and recorded in eCRF.
- ADVERSE EVENTS RECORDING: the status of unresolved AEs/SAEs at the discharge will be checked and any new AEs/SAEs occurred after the discharge will be recorded in the eCRF.

This safety follow-up call shall also be performed in case of premature discontinuation (7-10 days from the last administration intake).

If needed, according to the investigator's opinion, a follow-up visit can be performed.

### 7.1.4 Study restrictions and standardization

1. The following restriction must be applied during the study and must be checked at clinical unit from starting of Screening to discharge:
  - No smoking or intake of substances containing nicotine: within the entire study period.
2. The following restriction must be applied prior to the screening:
  - No strenuous activities: within 24h prior to the start of screening until the end of the visit.
3. The following restrictions must be applied during the treatment period (pre- and post-dose refer to the inhaled dose):
  - No food intake: within 10h pre-dose until 2h post-dose of study treatment drug. If needed, participants may consume prunes or prune juice to facilitate stool samples
  - No fluid intake: within 1h pre-dose and 1h post-dose of study treatment drug. Afterwards, in order to maintain adequate hydration, subjects should take at least 240 mL of water every 2h for the following 6h
  - No strenuous activities: within 24h pre-dose until Day 11
  - No intake of beverages or food containing alcohol: within 48h pre-dose until discharge on Day 11
  - No intake of beverages or food containing xanthine (coffee, tea, chocolate, cola), or grapefruit (neither fruit nor juice): within 48h pre-dose until discharge on Day 11. Decaffeinated products are permitted except during fasting periods
  - No intake of food containing poppy seeds: within 24h pre-dose until Day 11
4. The following restriction must be applied to prior to the screening and discharge:
  - No food intake: within 10h prior to the blood collection for the lab test.

If these restrictions are not respected, the visit can be rescheduled once and all the information regarding restriction(s) not respected, will be recorded in the eCRF. If the restrictions are again not respected, the visit will be performed anyway and all the information regarding restriction not respected will be recorded in the eCRF.

Clinical Study Code: CLI-06001AA1-02	Version No.: 1.0
EUDRACT No.: 2020-004201-31	Date: 19 October 2020

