### Treatment Period

During the treatment period, subjects will remain at the clinical site (all subjects will be treated at [REDACTED] site) from Day -1 (the day before the study drug administration) until the morning of Day 11. Each subject will fast from 10 hours pre-dose until 2 hours post-dose (between 2 hours post dose and discharge, standard meals will be provided at standard times as per site practice). They will be discharged after the 240h post-dose (i.v.) assessments are completed.

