### 7.2.5 Local Safety 12-Lead ECG

A local triplicate 12-lead digitalized Electrocardiogram (12-lead ECG) recording will be done and considered for safety purpose at Screening (before Blood pressure and blood sampling) to check the subject eligibility (according to exclusion criterion) and a local single 12-lead ECG will be performed on Day 1 of the study period at **predose and at 2,5 hours** after inhaled administration. No time deviations will be recorded for ECG.

Subjects should be resting in a quiet supervised setting with minimal stimulation (e.g. no television, loud music, computer games) and lay in a supine position for 5 minutes (whenever possible) before each measurement.

Below indications will be followed for Local ECG measurement at Screening:

- As for Inclusion Criterion no. 8, in case abnormalities are observed with Local ECG ( $40 \leq$  Heart rate  $\leq 110$  bpm,  $120$  ms  $\leq$  PR  $\leq 210$  ms, QRS  $\leq 120$  ms, QTcF  $\leq 450$  ms for males) subject will perform again the ECG measurement. If at that time the average of the triplicate ECG parameters is within the allowed ranges, subject can be included in the study, otherwise subject will be discharged and recorded as Screening Failure.

Below indications will be followed for local ECG measurement during the treatment period:

- A single 12-lead ECG measurement will be performed on Day 1, at predose and at 2 hours post dose (in resting conditions as much as possible)

The values of all ECG parameters and the overall ECG evaluation will be reported in eCRF, at Screening and the average will be used to assess the inclusion criterion.

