7.8 Definitions

7.8.1 Baseline and Change from Baseline

Baseline values are defined as the last evaluation before the first treatment dose (Inhalation).

For each of the above variable, change from baseline is defined at each post-dose as:

Post-dose value – baseline value.

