10.3 Vital Signs

For the purpose of safety analyses, the mean of triplicate measurements of systolic blood pressure (SBP) and diastolic blood pressure (DBP) will be used. The mean SBP and DBP values at baseline and at 2.5 hours post- dose will be summarized using descriptive statistics. Change from baseline to 2.5 hours post-dose in mean SBP and DBP will also be summarized.

Number and percentage of subjects with clinically relevant changes from baseline to 2.5 hours post-dose in SBP and DBP will be summarized. Clinically relevant changes are defined as:

- Change from baseline in SBP > 10 mmHg
- Change from baseline in DBP > 20 mmHg

10.4 12-lead Safety Electrocardiogram

Triplicate ECG measurements will be averaged on available values and the average value will be used to calculate summary statistics for heart rate (HR), PR interval (PR), QRS interval (QRS) and QTcF interval (QTcF)..

Baseline value (i.e. pre dose value) and 2.5 hours post dose will be summarized.

Number and percentage of subjects with clinically relevant change in HR at 2.5 hours post-dose defined as change from baseline > 20 bpm, will also be summarized.

The number and the percentage of subjects with QTcF abnormalities defined as:

- QTcF >450 ms,
- QTcF >480 ms
- QTcF >500 ms;
- change from baseline to 2.5 Hours post dose in QTcF >30 ms
- change from baseline to 2.5 Hours post dose in QTcF >60 ms;

will be summarized.

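### The plan does not say whether the only post-dose blood pressure and ECG come before or after the first meal, so a fasted baseline may be paired with a just-fed reading

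*Protocol*

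**What the plan says.** **Fast and meals.** Protocol 7.1.4 gives the restriction as "No food intake: within 10h pre-dose until 2h post-dose of study treatment drug" and adds that "pre- and post-dose refer to the inhaled dose". Section 3 (Treatment Period) says what follows: "between 2 hours post dose and discharge, standard meals will be provided at standard times as per site practice". The first meal is given no time relative to any assessment.

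**Readings.** Footnote b to the schedule in 7.1 places the single Day 1 ECG "for general safety at predose and at 2,5 hours post dose (inhaled administration"), and gives the same two times for blood pressure, measured in triplicate. Section 7.1.2 agrees: "A single 12-lead ECG measurement will be performed on Day 1, at predose and at 2,5 hours post dose". Section 7.2.5 gives 2.5 h in its first paragraph, but further down says "A single 12-lead ECG measurement will be performed on Day 1, at predose and at 2 hours post dose". Sections 7.2.4 and 7.2.5 standardise rest, supine posture and surroundings. Neither mentions food.

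**Analysis.** SAP 7.8.1 states: "Baseline values are defined as the last evaluation before the first treatment dose (Inhalation"). SAP 10.3 summarises blood pressure at baseline and 2.5 h, the change between them, and counts of changes above set limits. SAP 10.4 counts heart-rate flags "defined as change from baseline > 20 bpm", together with QTcF values and changes above set limits. Section 3 of the protocol describes an uncontrolled, single-dose study.

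**The concern.** Each planned change from baseline in blood pressure, heart rate or QTcF rests on two occasions. The first is inside the fast. The second is 30 minutes after the fast is lifted, and nothing in the documents says whether the subject has eaten by then. If some have and others have not, food state differs within a pair for some subjects and differs between subjects.

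There is no control group and no later scheduled reading, so a change caused by eating could not be separated from a drug effect. A rise in heart rate after food could produce a flag, and a fall in blood pressure after food could hide one. No section expressly asks for meal times to be recorded, so the point might not be recoverable afterwards. This is also the only scheduled blood pressure and ECG after an intravenous infusion that, according to section 1.3, has not previously been given to humans.

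**Working it through.** **1. Timeline.** The example clock in Protocol 7.2.1.1 has inhalation at 09:00.

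- Fast: 09:00 − 10 h = 23:00 the evening before, to 09:00 + 2 h = 11:00.
- Infusion: starts 09:00 + 1 h 45 min = 10:45, ends 11:00.
- Blood pressure and ECG at 2.5 h: 11:30, which is 45 minutes after the start of infusion.
- Gap from end of fast to reading: 30 minutes. The sampling table's last fasted mark is at 11:00.

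**2. How much of the gap is free.** Blood is due at 11:00, 11:05, 11:10 and 11:15 (each ± 2 min) and at 11:30 (± 5 min). Section 7.2 gives these draws priority. Section 7.2.4 asks for three blood pressure measurements within 5 minutes, before blood sampling, with 5 minutes supine beforehand whenever possible.

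- If readings start at 11:30, rest starts at 11:25, leaving 11:15 to 11:25 = 10 minutes.
- If the triplicate is finished by 11:30, it starts at 11:25 and rest at 11:20, leaving 11:15 to 11:20 = 5 minutes.

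So about 5 to 10 minutes are free. The window is longer if the readings run late, and sections 7.2.4 and 7.2.5 set no tolerance for them.

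**3. Illustration of size.** The documents contain no meal effect and no SD of change, so all shifts and SDs below are assumptions. The calculation also assumes no drug effect, normally distributed changes, and the same shift in all 8 subjects, which is the extreme case.

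Formulas: p = 1 − Φ((threshold − shift)/SD); P(at least 1 of 8) = 1 − (1 − p)^8.

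Worked case, heart rate, SD 8, shift +5: (20 − 5)/8 = 1.875, p = 0.0304, 1 − 0.9696^8 = 21.9%. With no shift: 20/8 = 2.5, p = 0.0062, giving 4.9%. Expected flags go from 8 × 0.0062 = 0.05 to 8 × 0.0304 = 0.24.

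Chance of at least one heart-rate change above 20 bpm:

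| SD of change (bpm) | no shift | +5 bpm | +10 bpm |
|---|---|---|---|
| 6 | 0.3% | 4.9% | 32.4% |
| 8 | 4.9% | 21.9% | 59.1% |
| 10 | 16.8% | 42.5% | 74.9% |

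Chance of at least one systolic change above 20 mmHg (the limit in Protocol 12.3.5):

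| SD of change (mmHg) | no shift | −5 mmHg | −10 mmHg |
|---|---|---|---|
| 8 | 4.9% | 0.7% | 0.1% |
| 10 | 16.8% | 4.9% | 1.1% |
| 12 | 32.4% | 14.0% | 4.9% |

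If only 2 of the 8 eat before the reading (again an assumption), the worked heart-rate case becomes 1 − 0.9938^6 × 0.9696^2 = 9.4% rather than 21.9%.

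**4. Which limits apply to blood pressure.** Protocol 12.3.5 uses more than 20 mmHg systolic and more than 10 mmHg diastolic. SAP 10.3 has these the other way round, and SAP section 12 declares no changes. At SD 10 mmHg with no shift, the chance of at least one systolic flag is 16.8% with a limit of 20 and 74.9% with a limit of 10. This discrepancy alone outweighs most of the shifts above and must be reconciled before any count is read.

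**The case against.** **No meal is scheduled in the gap, and there is little room for one.** This stands. The sampling and rest rules make eating before 11:30 unlikely where the timetable is kept. A reader might infer that the protocol feeds subjects before the reading; it does not. It permits food from 2 h and leaves the time to the site.

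**The ECG may be at 2 h.** This also stands. One line of section 7.2.5 puts it there, at the end of the fast. The heart-rate and QTcF parts then fall away, and blood pressure alone remains. The documents must settle which time is meant.

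**The size is assumed.** This is correct. The figures show direction and sensitivity and are not a forecast. Applying the shift to all 8 subjects conflicts with how narrow the window is.

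**A shift in standard errors.** A reader might go further and express the shift in mean heart rate as a number of standard errors at n = 8. The plan gives no footing for that: SAP 7.1 rules out tests and confidence intervals, and SAP 10.4 plans no summary of mean heart-rate change.

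**Matching food state does not make the comparison clean.** This is true. Section 7.1.4 has subjects drinking water from 1 h, and time of day, repeated venepuncture and the infusion itself also differ between the two readings. The change removes one non-drug influence and leaves the others.

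What survives is narrow: the order of meal and reading is unspecified, and specifying it costs almost nothing.

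**Conclusion.** The gap is real and minor. A fasted baseline may be paired with a reading taken shortly after food, in an unknown and probably small number of the 8 subjects. For blood pressure this follows from the text as it stands. For heart rate and QTcF it holds only if the ECG is at 2.5 h.

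The consequence is confined to descriptive change summaries and counts in an uncontrolled group. Absolute bioavailability and mass balance are unaffected. The documents do not support a claim that the safety results are biased, or by how much: the probabilities in the working rest on assumed shifts and SDs and on every subject being affected. They show only that a modest non-drug shift of either sign could add or remove a flag when n is 8. This is a cheap improvement, not a flaw that threatens the study's conclusions.

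**What to change.** Add one sentence to Protocol 7.1.2, 7.2.4 and 7.2.5 saying that the post-dose blood pressure and ECG are completed before the first post-dose meal, so that both readings of each pair share the same food state. The cost is a first meal up to about 30 minutes later, with no new assessment.

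If the order is not fixed, or subjects have already been dosed, the fallback is to record or retrieve the time of the first meal and show food state alongside the change tables in SAP 10.3 and 10.4.

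Two reconciliations belong with this change: the 2 h and 2.5 h statements for the post-dose ECG in Protocol 7.2.5, and the systolic and diastolic limits that differ between Protocol 12.3.5 and SAP 10.3.
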